#### 3.4 Endpoints/Outcomes Measurements

# 3.4.1 Primary outcome.

Primary end-point: Post-operative bariatric patients that use aromatherapy will have a greater decrease in mean nausea levels compared to control group.

# 3.4.2 Secondary outcomes

Secondary end-points: A decrease in the use of antiemetic medication administration in the post-operative bariatric patient population; determine if aromatherapy utilization for nausea is more beneficial with a particular post-operative bariatric patient population (sleeve gastrectomy, Roux-En-Y, revisional bariatric surgery).

#### 3.5 Consent/Assent

Informed written consent will be obtained by either the PI or SI. The PI or SI will provide consent document to all willing participants after they have met the inclusion criteria listed above and have not met any exclusion criteria. The participant will have an opportunity to view the consent, read the contents, and have time to ask any questions. If they are willing to be a participant in the study the consent will be signed and witnessed by the PI or SI. See attached Informed Consent Document from potential participants (refer to appendix C: Consent).

## 3.6 Monitoring Subjects and Criteria for Withdrawal of Subjects from the Study.

Participants may withdraw from the study at any time, as desired.

# 4 STATISTICAL CONSIDERATIONS/DATA ANALYSIS

# 4.1 Sample Size

To test the primary hypothesis that aromatherapy will lead to a decrease in post-operative nausea among patients undergoing laparoscopic/robotic sleeve gastrectomy, Roux-En-Y, and/or revisional bariatric surgery we will use a Pearson Chi-Square test for proportion difference. Assuming an expected incidence of nausea among controls of 80%, an alpha level of 5 percent, and a 1:1 treatment to control group ratio, we anticipate 90 subjects per group (n= 180 total) provides at least 80% power will to detect a statistically significant 20% reduction in the incidence of nausea among aromatherapy patients. The randomization scheme was calculated with SAS (ver.9.4., Cary, NC) using a two-group (treatment vs. placebo), simple randomization block (n=15) design. The total randomization scheme was increased to 180 (15 blocks of 12 patients) to allow for drop out and screen failures. Sample size will be increased to 180 subjects, this allows for a 20% (n=30) adm/screen fail/etc. error.

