Aromatherapy is the use of essential oils for the purposes of healing. It has been used for centuries to help relieve pain, kill bacteria, and promote health. It has been accepted as a part of nursing in many countries but only recently in the United States. Clinical aromatherapy is the controlled and therapeutic use of essential oils in the clinical setting for specific, measurable outcomes and is a natural therapy that is being used during hospitalization to improve symptoms (Johnson, 2016). According to Buckle (2009), "peppermint, spearmint, and ginger are the classic essential oils to inhale for nausea" (p. 402).

Lua and Zakaria (2012) reviewed five research articles which included 328 subjects who received essential oils via inhalation for the alleviation of nausea and vomiting. The results suggest that inhaled vapors of peppermint or ginger essential oils did reduce the incidence and severity of nausea and vomiting, decreased the utilization of antiemetic medication and improved patient satisfaction. Peppermint oil has been shown to be effective in the treatment of morning sickness, dyspepsia, gastrointestinal complaints due to its antispasmodic properties (Buckle, 2015 & Lua, 2012). Ginger has shown to be effective with motion sickness, pregnancy induced nausea and post-operative nausea (Buckle, 2015 & Lua, 2012).

A prospective exploratory study in 2015 utilized the produce QueaseEASETM for the treatment of post-discharge nausea in same day abdominal surgery patients (n=25). Ninety- six percent of participants had either a laparoscopic cholecystectomy or hernia repair. Fourty-seven episodes of post-discharge nausea was reported, and all of the subjects had a decrease in their nausea scale (0-10) after using the product and 22 of those 47 episodes (47%) reported a nausea scale of 0 after using the product. The mean decrease in nausea scale for the 25 participants was 4.78 (+2.12)

after using the QueaseEASE™ product (Mcilvoy, 2015). This study found that aromatherapy was an effective treatment for post-discharge nausea in same day abdominal surgery patients.

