# 4.2 Method of Data Analysis

Data will be presented as mean ± SD or frequency (percent), where appropriate. Group differences will be compared using Student's t-test, or chi-square tests of association, where appropriate. Data will be assessed for departures from normality with group comparisons adjusted accordingly. The primary hypothesis efficacy endpoint is incidence rate of nausea following surgery. Rates of nausea and 95% confidence intervals will be presented and group comparison will be via chi-square tests. The primary efficacy analysis will only include surgery groups sleeve gastrectomy and Roux-En-Y. However, to expand our knowledge regarding the effect of aromatherapy, we will recruit patients undergoing revisional bariatric surgery but these will only be considered for secondary analyses. As this is an RCT, we anticipate potential cofounders (e.g., gender, type of surgery, etc.) and effect modifiers to be distributed equally. However, in the event of a failed distribution of clinical or demographic characteristics, mixed effects modeling will be substituted to test the primary hypothesis. All analyses will be conducted using SAS (Ver.9.4, Carey, NC) with statistical significance considered as p≤0.05, two-tailed.

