# Data Collection Form A

intervention	
Nausea level before aromatherapy:	0 1 2 3 No Nausea Some Alot Severe
Date:/ Time:	— , s
Administer Aromatherapy product/ Intervent	
Aromatherapy product given:	Product A Product B
Date:/ Time:	— 4
Reassess nausea level after aromatherapy:	
Nausea level 5 minutes after aromatherapy:	0 1 2 3 No Nausea Some Alot Severe
Date:/ Time:	- .a
Did the patient request an antiemetic after the are	omatherany intervention?
YES NO	omaticapy mes content.
Date:// Time:	W4
xx	_ ,
	Add Patient Label

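### The primary hypothesis concerns a fall in the 0-3 nausea level, but the primary test is a chi-square on an undefined nausea rate; on the natural reading it ignores differences among scores 1, 2 and 3.

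*Combined protocol and SAP*

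**What the plan says.** **Hypothesis and endpoint.** Section 3.4.1 gives the primary endpoint as "Post-operative bariatric patients that use aromatherapy will have a greater decrease in mean nausea levels compared to control group". Hypothesis 1 says the same in the Abstract, where it is tied to the 0-3 scale, and in Section 1.2.

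**Data.** Data Collection Form A (Appendix D) records nausea before the product and again 5 minutes after it, each time on four ordered levels: "0 1 2 3 No Nausea Some Alot Severe".

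**Test.** For the primary hypothesis Section 4.1 says "we will use a Pearson Chi-Square test for proportion difference", with an "expected incidence of nausea among controls of 80" per cent and a 20% reduction. Section 4.2 says "The primary hypothesis efficacy endpoint is incidence rate of nausea following surgery" and continues: "Rates of nausea and 95% confidence intervals will be presented and group comparison will be via chi-square tests". Student's t-test appears in 4.2 only as a general option; the sentences about the primary endpoint assign the chi-square.

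**Not stated.** No section says which score counts as nausea, or at what time. The plan gives no reason for reducing the score to a proportion, and no expected distribution of scores.

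**The concern.** The test does not measure what the hypothesis is about. The product is given only after a first complaint of nausea (Sections 2.7 and 3.1), so nearly every treated patient is nauseated beforehand. A comparison of 80% with 60% therefore makes sense mainly as the proportion still at score 1 or more 5 minutes after the inhaler. On that reading a patient who goes from 3 to 1 counts the same as one who stays at 3.

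At stake is a missed effect. The trial could lower nausea levels, as hypothesis 1 predicts, and the primary test could fail to show it, although the forms already hold the information.

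**Working it through.** **1. The plan's own figure.** Inputs from 4.1 and 4.2: control rate 80%, 20% reduction, two-sided 5%, 90 per group.

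Power = Φ{[|p1 − p2|√n − 1.96√(2p̄(1 − p̄))] / √[p1(1 − p1) + p2(1 − p2)]}

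- 80% v 60%, n = 90, p̄ = 0.70: (0.20 × 9.487 − 1.96 × 0.648) / 0.632 = 0.99, so power is 83.9%. This agrees with the stated 80% or more.
- 80% v 60%, n = 75 (180 less the 30 losses allowed in 4.1, halved): (0.20 × 8.660 − 1.270) / 0.632 = 0.73, so power is 76.7%.
- 80% v 64% (20% read as relative), n = 90: 66.9%. The plan's figure therefore fits the absolute reading, which is used below.

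**2. A fall in severity only.** Assume controls at 20/40/25/15% over scores 0/1/2/3 and the active arm at 20/60/15/5%.

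- Control mean: 0.40 + 2 × 0.25 + 3 × 0.15 = 1.35.
- Active mean: 0.60 + 2 × 0.15 + 3 × 0.05 = 1.05.

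The mean level falls by 0.30, but both arms have 80% at score 1 or more. Simulated power at 90 per arm: chi-square 5%, tie-corrected Wilcoxon 57%.

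**3. A common shift.** Assume one odds ratio at every cut, set by 80% v 60%: (0.8/0.2)/(0.6/0.4) = 2.67. With controls at 20/40/25/15 the odds of scoring at least 1, 2 and 3 are 4, 0.667 and 0.176. Dividing each by 2.67 gives 60%, 20% and 6.2%, so the active arm is 40/40/13.8/6.2. The control split is an assumption, so it is varied. Simulated power, chi-square v Wilcoxon:

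| Control split 0/1/2/3 (%) | 90 per arm | 75 per arm |
|---|---|---|
| 20/60/15/5 | 84 v 91.5 | 77 v 86 |
| 20/40/25/15 | 84 v 95 | 77 v 90 |
| 20/20/30/30 | 84 v 95 | 77 v 91 |
| 20/70/8/2 (nearly all nauseated controls at 1) | 84 v 88.5 | 77 v 82 |

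In the first three rows the ordinal test gains about 7-11 points at 90 per arm and 9-15 at 75. In the last row it gains about 4-6.

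**4. Complete relief only.** Assume the product takes the same share of patients to 0 from every level and leaves the rest unchanged. Each probability above 0 is multiplied by 0.60/0.80 = 0.75, so the mean level falls by 25% and hypothesis 1 is still satisfied. Simulated power, chi-square v Wilcoxon:

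| Control split 0/1/2/3 (%) | 90 per arm | 75 per arm |
|---|---|---|
| 20/60/15/5 | 84 v 73 | 77 v 65 |
| 20/40/25/15 | 84 v 68 | 77 v 60 |
| 20/20/30/30 | 84 v 68 | 77 v 60 |

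The ordinal test now loses about 11-17 points.

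**5. Between these cases** (split 20/40/25/15, 90 per arm, chi-square 84%). If the log odds ratio at the upper cuts is 75% of that at the 0/1 cut, the Wilcoxon has 87%; at 50% it has 74%. If only score-1 patients move to 0, it has 31%.

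**The case against.** **The cut is not written down.** The Abstract also describes the primary outcome as an improved reported level. If the proportion means improved v not improved, a move from 3 to 1 is a success. A reader might infer that the plan scores every partial improvement as failure; the documents do not establish that. What stands is that the rate is undefined and that its most natural reading has this effect.

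**It follows from the endpoint conflict.** If the sponsor settles on mean level, Section 4.2 already lists a t-test, whose power under the common shift is 90-95% at 90 per arm for splits like the first three above. That is fair, but 4.1 sizes the trial on the chi-square and 4.2 names it for the primary endpoint, so both need changing. If the sponsor settles on a post-inhaler rate, the differences among scores 1-3 are still discarded.

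**The gain depends on the shape of the effect.** This stands in full. The plan supports neither a common odds ratio nor any control split. The systematic review quoted in Section 1.3 found no severity benefit beyond three minutes but more patients free of nausea, which leans towards the pattern in which the chi-square is stronger.

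**The earlier study of the same product.** Section 1.3 reports that all subjects improved but only "22 of those 47 episodes (47%) reported a nausea scale of 0 after using the product". A reader might infer that about half of all improvements would be lost here. That study was uncontrolled, used a 0-10 scale and counted episodes in 25 patients. It cannot size the loss between arms in this trial.

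**Conclusion.** The point holds as a mismatch between hypothesis and test, and it should be corrected. On the natural reading the chi-square cannot detect a fall in level that leaves the proportion at 0 unchanged.

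A reader might go further and infer that the plan simply forfeits 7 to 15 points of power. The documents do not support that as a general statement. The gain requires three assumptions: nausea means score 1 or more at 5 minutes, the odds ratio is common to all cuts, and the control split resembles the first three tabulated. It is smaller if nauseated controls nearly all score 1, and it reverses if the only effect is complete relief. The case for change therefore rests first on alignment with Section 3.4.1 and only second on power.

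The calculations use 90 and 75 per arm without baseline adjustment. Section 4.2 also excludes revisional patients from the primary analysis, so the number analysed, and the power of either test, will be lower to an extent that the plan does not allow one to calculate.

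**What to change.** - In 4.1 and 4.2, make the 5-minute 0-3 score the primary analysis, with arm and the Form A baseline score in the model: proportional odds, or an ANCOVA-type comparison of mean level. Report the effect with its 95% CI. Baseline belongs in the model because the hypothesis concerns a decrease.
- Name the proportion with score 0 at 5 minutes, with its 95% CI and chi-square, as a key secondary analysis. This covers the complete-relief pattern and defines the rate.
- Keep the enrolment of 180. In 4.1 restate power with the assumed control split, the assumed shape of effect, and the number in the primary analysis after the 30 losses and the exclusion of revisional patients.

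The cost is wording in the protocol and SAP; Form A already collects both scores, and no further patients or visits are needed. The drawbacks are that an odds ratio is slightly harder to explain than a rate, and that power is lower if the product's only effect is complete relief.

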#### ABSTRACT

**Title:** Effects of Aromatherapy in Decreasing Nausea Levels in the Post-operative Bariatric Patient Population on a Surgical Unit

Short Title: Effects of Aromatherapy on Nausea Levels

**Rationale:** Aromatherapy is the therapeutic use of essential oils from plants for the improvement of physical, emotional, and spiritual well-being. Healthcare providers play an important role in improving the care of patients with nausea. Aromatherapy is a complementary therapy that may help with post-operative nausea in the adult post-operative bariatric patient population.

**Purpose:** The purpose of this study is to evaluate the effects of aromatherapy intervention on nausea levels with post-operative bariatric patients once they are on the surgical unit.

**Objectives:** Hypotheses include the following: 1) Patients using aromatherapy with the initial episode of nausea on the surgical unit will have a greater decrease in mean nausea levels compared to control group. 2) The use of aromatherapy will decrease the utilization of antiemetic medication in the first 24 hours in the post-operative bariatric patient population.

Study Type: Single blinded, parallel arm, placebo- controlled, randomized clinical trial.

Study Design: Inclusion criteria includes: Patients ≥ 18 years of age admitted to the Surgical Unit who are experiencing an initial episode of nausea status post laparoscopic/ robotic sleeve gastrectomy, and/or laparoscopic/robotic Roux-En-Y (RNY) surgery, and/or revisional bariatric surgery; must be able to read and speak English; able to follow directions; bariatric surgeon is part of Inova Medical Group (IMG) and patient is an inpatient. Exclusion criteria include: Patients < 18 years of age; non-English speaking; not able to follow directions; inability to smell (anosmia); allergy to peppermint, spearmint, ginger and/or lavender; receiving bariatric surgery for gastroparesis; pregnant or breastfeeding; vulnerable subjects; receiving complementary therapy (healing touch and/or music therapy) or presently enrolled in another research study. The study location is the Surgical Unit at Inova Fair Oaks Hospital. The proposed sample size is 180 subjects.

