# 2.4 Number of Subjects

Total number of subjects is 180.

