#### 2.7 Inclusion Criteria

Inclusion criteria includes: patients  $\geq$  18 years of age admitted to the Surgical Unit who are experiencing an initial episode of nausea status post laparoscopic sleeve gastrectomy or laparoscopic Roux-En-Y (RNY) surgery and/or revisional bariatric surgery; must be able to read and speak English; able to follow directions; not allergic to peppermint, spearmint, ginger and/or lavender; bariatric surgeon is part of IMG group and patient is an inpatient.

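### Section 4.1 claims at least 80% power for 180 patients, but that 180 already includes 30 allowed losses and revisional patients left out of the primary analysis

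*Combined protocol and SAP*

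**What the plan says.** Section 4.1 assumes 80% nausea incidence in controls, 5% alpha and 1:1 allocation. It states that "90 subjects per group (n= 180 total) provides at least 80% power" "to detect a statistically significant 20% reduction in the incidence of nausea among aromatherapy patients".

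The same paragraph then describes 180 as an enlarged number: "The total randomization scheme was increased to 180 (15 blocks of 12 patients) to allow for drop out and screen failures", and "Sample size will be increased to 180 subjects, this allows for a 20% (n=30) adm/screen fail/etc. error".

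No other section adds patients on top. The abstract says "The proposed sample size is 180 subjects", section 2.4 says "Total number of subjects is 180", and section 3.3 randomises every subject on enrolment to reach 90 per group.

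On the population, section 2.7 admits "laparoscopic sleeve gastrectomy or laparoscopic Roux-En-Y (RNY) surgery and/or revisional bariatric surgery", and section 4.1 includes revisional patients in the powered hypothesis: "and/or revisional bariatric surgery we will use a Pearson Chi-Square test for proportion difference". Section 4.2 and the abstract's Statistical Methodology paragraph restrict the primary efficacy analysis to sleeve gastrectomy and Roux-En-Y and keep revisional patients for secondary analyses. No number or cap for revisional patients is given.

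**The concern.** An allowance for losses should leave the required number after the losses have occurred. Here the power is attached to the number before losses. Two groups draw on the same 180: the 30 the plan allows to be lost, and the revisional patients whom 4.2 excludes by design. Sections 4.1 and 4.2 also disagree on which patients the primary test covers.

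At stake is the stated chance of missing a real effect. Section 4.1 implies at most 20%. The margin above 80% power may be smaller than the losses already planned for, and 4.1 does not give the power that would remain.

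**Working it through.** **Inputs.** Control incidence 0.80, alpha 0.05, 1:1 allocation and Pearson chi-square are from 4.1; the two-tailed test is from 4.2. The 20% reduction has no stated scale, so both readings are tried: absolute (0.80 to 0.60) and relative (0.80 × 0.80 = 0.64).

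**Formula.** With n per group, difference d and mean proportion p̄:

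power = Φ{ [d − 1.96·√(2p̄(1−p̄)/n)] / √([p1(1−p1) + p2(1−p2)]/n) }

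**Reproducing the plan's figure (n = 90).**

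- Absolute: d = 0.20, p̄ = 0.70. The two standard errors are √(0.42/90) = 0.0683 and √(0.40/90) = 0.0667. Then (0.20 − 1.96 × 0.0683)/0.0667 ≈ 0.99, and power = 83.9%. The claim is met.
- Relative: d = 0.16, p̄ = 0.72. Power = 66.9%, and 123 per group would be required. The claim is not met.

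At two-sided 5%, only the absolute reading reproduces the statement. It is used from here.

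**Smallest n for 80%.** (1.96·√0.42 + 0.8416·√0.40)² / 0.20² = (1.270 + 0.532)² / 0.04 ≈ 81.2, so 82 per group, or 164 in all. The margin is 180 − 164 = 16 patients (16/180 = 8.9%).

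**The allowance.** 180 − 30 = 150, and 30/150 = 20%, so the plan's two figures agree on a base of 150. If 20% were meant of 180, it would be 36, leaving 144.

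| Analysed | Per group | Missing from 180 | Power, formula | Power, exact enumeration |
|---|---|---|---|---|
| 180 | 90 | 0 | 83.9% | 84.2% |
| 164 | 82 | 16 | 80.4% | 80.7% |
| 162 | 81 | 18 | 79.9% | 80.2% |
| 160 | 80 | 20 | 79.4% | 80.1% |
| 150 | 75 | 30 | 76.7% | 76.8% |
| 144 | 72 | 36 | 75.0% | not run |

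Exact enumeration of the uncorrected Pearson test falls to 79.5% at 79 per group, so on that method the margin is 180 − 160 = 20.

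**Revisional patients.** The documents give no share. Section 1.3 describes the hospital's caseload as sleeve gastrectomy and Roux-En-Y only, which may mean the share is small. The shares below are assumptions, shown for range.

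| Assumed revisional share | Only loss, taken from 180 | Taken from the 150 left after 30 losses |
|---|---|---|
| 5% | 82.0% (171 analysed) | 74.6% (142.5) |
| 10% | 79.9% (162) | 72.2% (135) |
| 20% | 75.0% (144) | 67.0% (120) |

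**The case against.** The sentence in 4.1 is true as arithmetic: 90 per group does give at least 80% power on the absolute reading. On this view the fault is one of labelling, because the text does not say whether 180 is the randomised or the evaluable number. The shortfall is also small, about 3 points with all 30 lost (about 2 with an unpooled variance, 78.2%). Loss after treatment may be slight, since the outcome is taken 5 minutes after a single use, and no analysis set is defined that removes all 30. The threshold depends on method: 16 by the standard formula, 20 by exact enumeration, 22 with an unpooled variance (79 per group). The larger falls rest on assumed revisional shares.

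Much of this is fair. The size is modest on the allowance alone, 82 per group should be labelled as the standard-formula figure, and actual losses may be fewer than 30. But 4.1 says the randomisation scheme itself was enlarged for these losses and 3.3 randomises on enrolment, so the plan places them inside the 180. None of the two-sided methods above reaches 80% at 75 per group, and every threshold is below 30. The conflict between 4.1 and 4.2 over the primary population remains whatever the revisional share.

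**Conclusion.** The concern holds. The stated power is right only if nearly all 180 patients enter the primary analysis, while the plan allows for 30 who may not and excludes revisional patients by design. The margin is 16 patients by formula and 20 by exact enumeration, roughly half to two-thirds of the allowance. With the full allowance used, power is about 77%, so the chance of missing a true fall from 80% to 60% is about 23% rather than at most 20%. Revisional patients outside the 30 would raise that by an amount the documents do not allow one to fix. If 4.1's wider population governed instead of 4.2's, the 77% would still apply.

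This rests on the absolute reading, which favours the plan; on the relative reading power is 66.9% even with all 180 analysed and 58.9% with 150. It also applies only to the incidence endpoint of section 4. Section 3.4.1 names the mean decrease in nausea level as primary, and no sample size is given for that.

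**What to change.** Reword 4.1 along these lines, once the team has confirmed the absolute scale and that incidence is the endpoint being powered:

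> 180 patients will be randomised (90 per group). For an absolute reduction from 80% to 60% (Pearson chi-square, two-sided 5%), power is about 84% if all 180 are in the primary analysis. By the standard formula, 82 evaluable sleeve gastrectomy or Roux-En-Y patients per group give 80% power. If the full allowance of 30 is used, 150 (75 per group) remain and power is about 77%.

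Also in 4.1, limit the primary-hypothesis population to sleeve gastrectomy and Roux-En-Y, to match 4.2. State the expected revisional share of the 180, whether those patients count against the 30, and the resulting power.

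The cost is wording plus one planning figure from the team. The 180, the blocks and the randomisation list do not change. The stated power becomes less favourable, and rewording recovers none of it. If the team prefers to protect 80%, keeping 164 evaluable after a 20% loss would take 164/0.80 = 205 patients in the two primary-analysis surgery groups; that is a separate choice.

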#### 3.3 Randomization

Upon enrollment in the trial, each subject will be randomized to one of two treatment groups: Product A (aromatherapy inhaler product), Product B (Placebo product: inhaler with distilled water). Each product will look the same. SAS will be used to generate the randomization table using random numbers to determine which treatment subject #1 will receive; subject #2 will receive, etc., resulting in a total of 90 subjects for each treatment group. The randomization scheme will be located in a secured location in the pharmacy department and access will be granted to Pharmacy and designated research team members.

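### Randomisation is not stratified by surgery type: a minor, cheaply avoided source of chance imbalance where surgery type is used in the analysis

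*Combined protocol and SAP*

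**What the plan says.** Sections 3.3 and 4.1 describe a single list. Section 3.3 has one SAS table in order of subject number, "resulting in a total of 90 subjects for each treatment group". Section 4.1 describes it as "using a two-group (treatment vs. placebo), simple randomization block (n=15) design" and gives 15 blocks of 12. Neither section names a stratification factor or separate lists by operation.

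Surgery type is then used in three ways:

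- **Primary set.** Section 4.2, like the statistical methodology in the Abstract, states: "The primary efficacy analysis will only include surgery groups sleeve gastrectomy and Roux-En-Y". Revisional patients are recruited for secondary analyses only. Section 4.1, however, words the primary hypothesis so that revisional surgery is part of it.
- **Confounder.** Section 4.2 adds: "we anticipate potential cofounders (e.g., gender, type of surgery, etc.) and effect modifiers to be distributed equally". If a clinical or demographic characteristic turns out unevenly distributed, a mixed effects model replaces the primary test. No threshold is given.
- **Comparison.** Sections 1.1 and 3.4.2 make the effect by surgery type a secondary aim and end-point. The Abstract calls it tertiary.

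Consent is taken before surgery on the day of the operation (Abstract; section 2.2), and section 3.3 randomises on enrolment. The scheduled operation is therefore known at allocation.

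**The concern.** Blocks of 12 hold the arms at 6:6 in list order, whatever operation each patient has. Removing revisional patients takes out whichever list positions they happened to fill, so the primary set is 1:1 only on average. Nothing holds the mix of sleeve and Roux-En-Y equal between arms, or the split within any one type.

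Three things are at stake: chance imbalance on a factor the plan itself calls a confounder, a greater likelihood that the primary model is changed after the data are seen, and uneven splits in what may be the smallest surgery group. All three can be reduced using information already available at allocation.

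**Working it through.** **1. The plan's own figure.** Inputs from section 4.1: "Assuming an expected incidence of nausea among controls of 80" per cent, a "statistically significant 20% reduction in the incidence of nausea among aromatherapy patients", "an alpha level of 5 percent, and a 1:1 treatment to control group ratio", and 90 per group. From section 4.2: "with statistical significance considered as p≤0.05, two-tailed".

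Power = Φ{[Δ − 1.96·√(2p̄(1−p̄)/n)] / √([p₁(1−p₁)+p₂(1−p₂)]/n)}

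With 80% v 60% and n = 90: [0.20 − 1.96 × 0.0683] / 0.0667 = 0.99, so power is 83.9%. The claim of at least 80% reproduces on the absolute reading without continuity correction. The relative reading (80% v 64%) gives 66.9% and does not reproduce. The absolute reading is used below.

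**2. Arm sizes in the primary set.** The documents give no surgery mix, so the revisional share f is assumed. With 90 per arm, the arm-size difference after removing revisional patients has variance 180·f(1−f). For f = 10% that is 16.2 (SD 4.0); for f = 20% it is 28.8 (SD 5.4).

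**3. Surgery mix in the primary set.** If q is the sleeve share and m the arm size, the SE of the between-arm difference in share is √(2q(1−q)/m). For a 60/30/10 mix (sleeve/Roux-En-Y/revisional), q = 60/90 = 0.667 and m = 81, so SE = √(2 × 0.222/81) = 0.074. Then P(difference ≥ 10 points) ≈ 2Φ(−0.10/0.074) ≈ 0.18.

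Simulation of the stated scheme (20,000 trials per mix, 180 patients, 15 blocks of 12) agrees:

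| Assumed mix | Sleeve share differs ≥ 10 points | Arm sizes differ ≥ 6 | Revisional split 60:40 or worse |
|---|---|---|---|
| 60/30/10 | 17.5% | 16.8% | 41.5% |
| 50/35/15 | 21.1% | 25.4% | 29.1% |
| 70/20/10 | 12.7% | 17.0% | 40.8% |
| 45/45/10 | 20.0% | 16.7% | 40.9% |
| 50/30/20 | 21.6% | 30.7% | 20.2% |

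**4. Cost to the primary test.** Mean power over simulated lists, against an exact 1:1 split of the same patients:

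| Revisional share | Patients kept | Mean power, simulated | If exactly 1:1 |
|---|---|---|---|
| 10% | about 162 | 79.8% | 79.9% |
| 20% | about 144 | 74.9% | 75.0% |
| 30% | about 126 | 69.1% | 69.2% |

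The loss from imbalance is at most about 0.1 point. For the estimate, assume nausea rates differ by 10–20 points between sleeve and Roux-En-Y. A 10-point gap in sleeve share then shifts the treatment difference by 0.10 × 10 to 0.10 × 20 = 1 to 2 points, against an SE of √(0.40/81) = 7.0 points.

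**5. What stratified lists would gain.** With three lists in mixed blocks of 4 and 6, and all 180 counted, the first two frequencies in step 3 fall to 0.0% and the third to 0.7% or less. But product is given and nausea scored only in patients who become nauseated on the unit (section 3.1). For the 60/30/10 mix, with an assumed share scored (single list → stratified lists):

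| Share scored | Arm sizes differ ≥ 6 | Revisional 60:40 or worse | Sleeve share differs ≥ 10 points |
|---|---|---|---|
| 80% | 36% → 28% | 49% → 18% | 23% → 1% |
| 60% | 42% → 39% | 57% → 38% | not run |
| 33% | 37% → 37% | 70% → 65% | 44% → 37% |

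**The case against.** The strongest reply is that this is a design preference. Unstratified permuted blocks are an accepted choice for a single-site trial of 180. Excluding patients on a factor fixed before randomisation leaves a valid randomised comparison. Expecting equal distribution is correct as a statement about averages. Section 4.2 already offers a model for imbalance, and pre-specified adjustment could handle surgery type without three lists. The surgery-type comparison is limited mainly by subgroup size, which stratification does not increase.

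Most of this stands, and it is why the point is minor. What it does not answer is that the fallback in section 4.2 is triggered by the data with no threshold, so a chance imbalance in surgery type can change the primary model. Nor does it give a reason to leave that imbalance open when the operation is known at allocation.

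A reader might infer that dropping revisional patients biases the primary test or raises its type I error. It does neither. A reader might also blame the power figures in step 4 on the list. The fall from 83.9% comes from having fewer patients, which stratification does not restore. Nor can one say that stratified lists would balance the analysed patients: step 5 shows the gain shrinking as fewer are scored.

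**Conclusion.** The point holds as a minor, inexpensive improvement. The single list secures 1:1 over the 180 randomised patients, but not in the primary set of section 4.2 or within any surgery type. The primary test remains valid and loses at most about 0.1 point of mean power to unequal arms. The consequences are chance imbalance in surgery type (a gap of 10 points or more in sleeve share in about 13–22% of trials), a higher chance of the undefined model switch, and a revisional group split 60:40 or worse in about 20–42%.

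The frequencies rest on assumed mixes of 45–70% sleeve, 20–45% Roux-En-Y and 10–20% revisional, with everyone randomised counted. That the list is unstratified is read from the silence of sections 3.3 and 4.1; some appendix pages were not available. If section 4.1 governs and revisional patients are in the primary analysis, the point about arm sizes in the primary set falls away. The confounder and surgery-type points remain.

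**What to change.** - **Sections 3.3 and 4.1:** replace the single list with separate permuted-block lists for sleeve, Roux-En-Y and revisional surgery, in mixed small even blocks such as 4 and 6. Pharmacy holds them and assigns by scheduled operation. Delete the word *simple*, which conflicts with a blocked design.
- **Section 4.2:** pre-specify a primary comparison stratified by surgery type, for example Cochran-Mantel-Haenszel for the binary end-point given there, so that imbalance in surgery type no longer changes the model. The trigger stays open for gender and other characteristics unless it is also defined or removed.
- **Sections 4.1, 4.2 and the Abstract:** reconcile whether revisional patients are in the primary analysis.
- **Limit:** state that stratification balances those randomised, and only partly those who become nauseated and are scored.

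The cost is one re-run of the SAS program and three lists instead of one. Pharmacy must check the scheduled operation before assigning, and a patient whose operation changes stays in the original stratum. If enrolment has begun and the list cannot be changed, the stratified analysis alone is still worth pre-specifying.
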